2.1.3.1 Primary efficacy endpoint (Phase 2 only)

The primary efficacy endpoint is ORR, defined as the proportion of patients with CR (including sCR), VGPR or PR as BOR as assessed by the investigator. BOR will be derived using disease assessments (overall response CRF page) from the start of treatment through the entire study excluding any assessments performed after disease progression (that is confirmed), the cutoff date or following the start of further therapies for MM (see Figure 1). The ordering of evaluations from best to worse is: sCR, CR, VGPR, PR, MR, stable disease (SD), progressive disease (PD), not evaluable (NE). BOR for patients without response assessment will be 'Not evaluable'. BOR will be the best sequential response based on the investigator's disease assessments as determined by the criteria in Table 3. In addition, the following rules will be applied:

- BOR will be NE for patients who received at most 2 isatuximab administrations with investigator assessment of response of SD or better at Cycle 1 or end of treatment.
- BOR will be PD for patients without response assessment who received 1 cycle of treatment and died due to PD or had symptomatic deterioration within 30 days of last study treatment administration.

Symptomatic deterioration will not be considered as progression in the primary analysis of ORR.

Table 3 - Sequential response determination for investigator response assessment

Overall response at Cycle n	Overall response at Cycle n+1 ^a	Sequential response
sCR	sCR	sCR
CR	sCR	CR
sCR	CR	CR
CR	CR	CR
sCR/CR	VGPR	VGPR ^b
sCR/CR	PR	PR
VGPR	sCR/CR/VGPR	VGPR ^b
VGPR	PR	PR

Overall response at Cycle n	Overall response at Cycle n+1 ^a	Sequential response
PR	sCR/CR/VGPR/CR/PR	PR
sCR/CR/VGPR/PR	NE/No further evaluation/SD/PD	MR ^c
MR	Any	MR
Any	MR	MR
NE/SD/PD	sCR/CR/VGPR/PR	MR ^c
NE/PD/SD	SD	SD
SD	No further evaluation/NE/PD	SD
NE	SD	SD
PD	No further evaluation/NE	unPD ^e
PD	PD	PD
NE	PD	unPD ^e
NE	No further evaluation	NE
No evaluation ^d		PD ^d

a Disease assessment are planned to be performed every cycle. Disease assessment performed after the start of new anticancer treatment will be excluded from the derivation of BOR.

b Sequence provided for programming purpose.

[figure not shown]
c Unconfirmed PR or CR will be considered MR.

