2.1.3.2 Secondary efficacy endpoints

Secondary efficacy endpoints are defined below.

[figure not shown]
- CBR: defined as the proportion of patients with CR (including sCR), VGPR, PR or MR as assessed by investigators using the IMWG response criteria.
- DOR: DOR is defined as the time from the date of the first response (≥PR) that is subsequently confirmed, to the date of first documented PD or death (if reported before the analysis cutoff date or the date of initiation of a new anticancer treatment), whichever happens earlier. In the absence of the confirmation of subsequent disease progression or death before the analysis cut-off date or the date of initiation of a further anticancer treatment, the DOR will be censored at the date of the last valid disease assessment not showing disease progression performed prior to initiation of a further anticancer treatment and the analysis cut-off date, whichever is earlier. DOR will not be calculated for patients that do not achieve a PR or better.
- TTR: defined as time from randomization to first response (PR or better) that is subsequently confirmed.
- PFS: defined as the time interval from the randomization date to the date of the first documented disease progression that is subsequently confirmed or the date of death due to any cause, whichever comes first. For patients who did not experience documented disease progression or death before the analysis cut-off date or the date of initiation of new anticancer treatment, PFS will be censored at the date of the last valid disease assessment not showing disease progression performed prior to initiation of a further anticancer treatment or the analysis cut-off date, whichever comes first. Date of PFS event/censoring relative to date of further anti-myeloma therapies and cutoff date are illustrated in [Figure 2](#). In addition, patient without PFS event (death or documented disease progression) and without any valid post-baseline disease assessments will be censored at the randomization date. Patients with death and time between the last post-baseline assessment and death >2 cycles will be censored at the date of last valid assessment (ie, not equal to NE). Subgroup analysis for variables defined in [Table 4](#) will be performed.

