2.5.3 Missing data

The analyses and summaries of continuous and categorical variables will be based on observed data only. Percentages will be calculated using as the denominator the number of patients with a non-missing observation in the considered population. When relevant, the number of patients with missing data will be presented.

When incomplete or missing dates were found in the eCRF, attempts were made to retrieve the complete date, especially for dates within the month prior to first dose. However, if some dates remain incomplete, the following rules will be applied:

Handling of disease characteristics missing/partial dates (if not otherwise specified below)

- If the day is missing, it will be imputed to be 1.
- If the month is missing, it will be imputed to be 1 (only for medical history variables).
- If the year is missing, no imputation will be performed.

Handling of medication (other than anticancer treatment) missing/partial dates

No imputation of medication start/end dates or times will be performed. If a medication date is missing or partially missing and it cannot be determined whether it was taken prior or concomitantly, it will be considered a prior, concomitant, and post-treatment medication.

Handling of post anti-myeloma treatment missing/partial dates

For post anti-myeloma treatments, if the anticancer treatment start date is missing, it will be imputed as follows:

- If the medication start day and month are missing and the medication start year is the same as treatment end year, the medication start date will be set equal to treatment end date + 1.
- If the medication start day and month are missing and the medication start year is after the treatment end year, the medication start day and month will each be set to 01.
- If the medication start day is missing and medication start year and month is the same as the treatment end year and month, the medication start day will be set equal to the treatment end day + 1.
- If the medication start day is missing and medication start month is before the treatment end month and the medication start year is the same as treatment end year, the medication start day will be set to 01.
- If the medication start day is missing and the medication start month is after the treatment end month and the medication start year is the same as treatment end year, the medication start day will be set to 01.

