- If the medication start day is missing and the medication start month is not missing and the medication start year is after the treatment end year, the medication start day will be set to 01.
- If the medication start day, start month and start year is missing, the medication start date will be set equal to the treatment end date + 1.

No imputation will be done for the missing/partial end date.

Handling of adverse events with missing or partial date of onset

Missing or partial adverse event onset dates (occurrence or becoming serious) will be imputed so that if the partial adverse event onset date information or visit number does not indicate that the adverse event started prior to or after treatment, the adverse event will be classified as treatment-emergent. In case of AEs worsening during the study, the emergence will also be based on the cycle of worsening. No imputation of adverse event end dates will be performed. These data imputations are for categorization purpose only and will not be used in listings. No imputation is planned for date of adverse event resolution.

Handling of death with missing or partial date of death

The imputation for missing or partial death date will proceed as follows:

- If the death day is missing and the death month and year are the same as the last month and year the patient was last known to be alive, the death day will be set equal to the last day the patient was known to be alive + 1.
- If the death day is missing and the death month is after the month the patient was last known to be alive and the death year is the same as the year the patient was last known to be alive, the death day will be set to 01.

- If the death day and month are missing and the death year is the same as the year the patient was last known to be alive, the death date will be set equal to the date the patient was last known to be alive + 1.
- If the death day and month are missing and the death year is after the year the patient was last known to be alive, the death day and month will both be set to 01.

If the date the patient was last known to be alive is partial or missing, no imputation for missing or partial death date will be performed. The last date the patient was known to be alive is the last of: date of last dose, date of last visit performed (when the patient is known to be alive according to subject vital status), date of last laboratory assessment, date of last vital signs.

Handling of adverse events with missing grade

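### Partial or missing start dates of further therapy are imputed to the earliest post-treatment day, which can erase a progression first documented after treatment end and censor the patient in PFS and DOR

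*SAP*

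**What the plan says.** **Imputation (SAP 2.5.3, post anti-myeloma treatment dates).** The start of further therapy is set as follows:

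- Day missing, same month and year as treatment end: "the medication start day will be set equal to the treatment end day + 1".
- Day missing, recorded month later than that of treatment end: "the medication start day will be set to 01". This applies within the same year, and a later year with a known month is treated the same way.
- Day and month missing, same year as treatment end: "the medication start date will be set equal to treatment end date + 1". If the year is later, the start is 1 January.
- Date fully missing: "the medication start date will be set equal to the treatment end date + 1".

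**Use of that date (SAP 2.1.3.2).** In PFS, a progression or death is an event only when it comes before both the cut-off and any new anticancer therapy. A patient with no such event is "censored at the date of the last valid disease assessment not showing disease progression performed prior to initiation of a further anticancer treatment"; an earlier cut-off takes the place of the therapy start. DOR carries the same condition on its event and the same censoring date. SAP 2.1.3.1 derives best overall response "excluding any assessments performed after disease progression (that is confirmed), the cutoff date or following the start of further therapies for MM".

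**Nothing that overrides it.** SAP 2.5.2, on data handling for secondary efficacy variables, is marked not applicable. The notes to Figure 1 in SAP 2.1.3.1, written for best response, keep a progression first documented before new therapy even if it is confirmed afterwards. SAP 2.1.10 lists a relapse/progression date among the items on the further-therapy eCRF page, but the imputation rule does not use it.

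**The concern.** Further therapy in myeloma is usually started because the disease has progressed, so the true order is progression first, new therapy second. The imputation always picks the earliest admissible day and can reverse that order. An observed event then becomes a censoring shortly before that event. This falls on patients who progress and switch quickly, so the censoring is informative and pushes the Kaplan-Meier estimates of PFS and DOR upward. With at most 35 patients per arm, a few converted events could visibly move a median.

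The design produces such patients. Protocol 12.4.3 places the end-of-treatment assessment 30 days after the last dose, or before further therapy if that is sooner. Protocol 6.6.1 has patients who stop without progression assessed monthly until progression or new therapy. Both can document a first progression after the last dose and close to a switch.

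**Working it through.** The plan states no figure to reproduce here, so the check applies the date rules directly. *Treatment end date* is taken as the last dose. A progression (PD) counts as lost if it falls on or after the imputed start.

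**Worked cases (2019)**

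| Last dose | First PD | True start | Missing | Imputed start | PD |
|---|---|---|---|---|---|
| 1 Mar | 15 Mar | 25 Mar | day | 2 Mar | lost |
| 15 Mar | 14 Apr | 20 Apr | day | 1 Apr | lost |
| 15 Mar | 29 Mar | 20 Apr | day | 1 Apr | kept |
| 15 Mar | 12 Jun | 5 Jul | day | 1 Jul | kept |
| 15 Mar | 12 Jun | 5 Jul | day and month | 16 Mar | lost |
| 15 Mar | 1 Mar | 25 Mar | day | 16 Mar | kept |

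The last row shows why on-treatment progression is safe: when new therapy begins after treatment end, the imputed start is never earlier than treatment end + 1. (SAP 2.5.3 has one more branch, for a recorded month before the treatment-end month. It concerns therapy begun while study treatment was still running and is left aside.)

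**How often, by lag.** Let *g* be the days from first PD to the true start. The documents give no such interval, so *g* is an assumption, varied from 3 to 30 days. Last dose was run over 730 consecutive dates, with PD 14 days later.

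*Only the day missing.* PD is lost exactly when PD and therapy start share a calendar month. In a month of N days this holds for N − g PD days. Over 24 months totalling 730 days the count is 730 − 24g, as long as g does not exceed the shortest month. For g = 30 only the fourteen 31-day months contribute, one day each.

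*Day and month missing.* PD is kept only if PD and therapy straddle a new year, which gives (730 − 2g)/730.

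| g (days) | Day missing: lost | Day and month missing: lost |
|---|---|---|
| 3 | 658/730 = 90% | 724/730 = 99% |
| 7 | 562/730 = 77% | 716/730 = 98% |
| 14 | 394/730 = 54% | 702/730 = 96% |
| 21 | 226/730 = 31% | 688/730 = 94% |
| 30 | 14/730 = 2% | 670/730 = 92% |

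With the date fully missing, every PD after treatment end is lost. The rounded percentages are the same with PD 30, 60 or 90 days after the last dose. With PD on the last-dose date or 14 days before it, the loss was 0% in every branch. All these are shares of patients who have an incomplete start date, not of the trial population.

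**The case against.** The strongest reply is that the exposed group may be small or empty.

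- Treatment continues until progression. Day 1 samples precede dosing, and the study flowchart notes say that awaiting results must not hold up the next cycle. Biochemical progression needs two consecutive assessments, while PFS takes the first documented date. Many progressions will therefore be dated on or before the last dose, where nothing is lost.
- SAP 2.5.3 says that complete dates were sought, though it stresses dates just before first dose.
- SAP 2.4.4.2 excludes hypothesis tests on secondary endpoints, so PFS and DOR are descriptive.
- The SAP does not define *treatment end date*. A date later than the last dose would protect more progressions.
- The PFS illustration, Figure 2, is not reproduced in the available text and could not be checked.

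All of this stands, and it limits the size and priority of the point. It does not make the rule give the right event status for a patient who is exposed.

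A reader might infer more than the documents support. The rule does not delete every progression in the month of the switch: those documented on or before treatment end survive. Nor is an effect on the ORR test shown: best response uses the same therapy start date, but dropping a progression does not turn a non-responder into a responder. The rule is identical across arms, and no between-arm bias is shown.

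**Conclusion.** The point holds for progression first documented after treatment end in patients whose further-therapy start date is partial or missing. For them, SAP 2.5.3 and 2.1.3.2 together can drop a progression that truly preceded new therapy and censor the patient at the last assessment without progression. The bias in PFS and DOR is upward.

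With only the day missing, the loss is confined to a progression in the same calendar month as the therapy start: about 90% of post-treatment progressions at a 3-day lag, falling to 2% at 30 days. With day and month missing it can reach across the year (99% to 92%). With the date fully missing it is complete. These shares rest on assumed lags and on reading treatment end as last dose. The effect on a median cannot be sized, because the number of incomplete dates is not given, and it could be negligible. This is a low-cost correction to descriptive endpoints, not a threat to the primary comparison.

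**What to change.** In SAP 2.5.3, for partial and fully missing start dates alike:

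- Impute the later of the current value and the first documented progression date + 1, where the recorded month or year allows it.
- If progression falls on the last day of the recorded period, set the start to the progression date and count a same-day progression as an event. Otherwise the requirement that progression come before new therapy would still remove it.
- Define *treatment end date*.
- Report the number of imputed start dates per arm.
- Keep the current rule as a sensitivity analysis for PFS and DOR.

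The cost is a few lines in SAP 2.5.3, a small change to the derivation code, one count per arm and one additional run. Complete dates are untouched. The drawback is that the floor uses the outcome to set the censoring date and assumes therapy followed progression. The sensitivity analysis shows how much depends on that assumption.

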2.5.4 Windows for time points

Laboratory data

A protocol planned laboratory test is considered to have occurred during a cycle if the date of sampling is after ($>$) the first day of the cycle, but prior to or equal (\leq) to the first day of the next cycle. For unscheduled tests, a test is considered to have occurred during a cycle if the date of sampling is equal to or after (\geq) the first day of the cycle, but prior ($<$) to the first day of the next cycle.

2.5.5 Unscheduled visits

Unscheduled visit measurements of laboratory data, vital signs and ECG will be used for computation of worst values and/or grades.

2.5.6 Pooling of centers for statistical analyses

Data from all sites will be pooled together for analyses.

2.5.7 Statistical technical issues

Not applicable.

3 INTERIM ANALYSIS

For Phase 2 part, a formal interim analysis of response rate (including confirmed and unconfirmed responses) will be performed when the first 15 randomized patients in each arm completed 2 cycles of treatment or permanently discontinue treatment. The purpose of the analysis is to stop combination arm early for futility.

The analysis will include the first 15 randomized patients from each arm in the ITT population. Given the observed response rate (including confirmed and unconfirmed responses) from each combination arm, and assuming the numbers of response follow binomial distribution with response rate=20% in control arm, and 50% in combination arm for the remaining 20 patients in each arm, the conditional power can be calculated based on 1-sided Fisher's exact test at 0.05 significance level (for each combination arm vs. control arm separately) at the end of the trial. If the conditional power is <30% for a combination arm, the arm will be stopped early for futility. The detailed decision rule of whether to continue or stop the arm is included in [Appendix B](#). R-code for calculating conditional power is included in [Appendix C](#).

The analysis will include the following parameters/analyses (defined in [Section 2](#)): response rate (including confirmed and unconfirmed responses), demographics and baseline characteristics, prior or concomitant medication, AEs (TEAE, death, SAE, TEAE leading to discontinuation and IR), laboratory variables (abnormality of hematological and chemistry test), PK NCA after first administration and ADA based on available data.

In addition, formal safety review by data monitoring committee (DMC) are planned approximately every 3 months to regularly monitor unblinded patient safety data (all meetings), unblinded efficacy data (except the 1st DMC meeting) and quality of trial conduct. More details on formal safety reviews and on interim analyses are given in the DMC charter.

4 DATABASE LOCK

The database will be locked when clinical review of the database has been completed and all critical queries have been resolved.

5 SOFTWARE DOCUMENTATION

All summaries and statistical analyses, except for biomarker analysis, will be generated using SAS® Version 9.4 or higher. Biomarker analyses will be performed using R software Version 3.4.0 or above.

7 LIST OF APPENDICES

[Appendix A](#): Generic ranges for hematological and biochemistry

[Appendix B](#): Interim analysis decision boundary

[Appendix C](#): R code for conditional power and stopping boundary calculation

Appendix A Generic ranges for hematological and biochemistry

Table 11 - Generic ranges for hematological parameters

Test	Gender	Unit	Lower/Upper limit of normal
Hemoglobin	F	g/L	120 - 160
Hemoglobin	M	g/L	135 - 175
Lymphocytes		10 ⁹ /L	1 - 2
Neutrophils		10 ⁹ /L	1.8 - 3.15
Platelets		10 ⁹ /L	150 - 350
Leukocytes		10 ⁹ /L	4.5 - 11
Eosinophils		10 ⁹ /L	0 - 0.4
Basophils		10 ⁹ /L	0 - 0.15
Monocytes		10 ⁹ /L	0.18 - 0.5
Hematocrit	M	ratio	0.41 - 0.53
Hematocrit	F	ratio	0.36 - 0.46
Erythrocytes	F	10 ¹² /L	4 - 5.2
Erythrocytes	M	10 ¹² /L	4.5 - 5.9
INR		ratio	0.8 -1.2

Based on Kratz et al. (3)

[figure not shown]
The current list of generic ranges for biochemistry parameters (for adults) is provided in the table below:

Table 12 - Generic ranges for biochemistry parameters

Test	Unit	Lower/Upper limit of normal
Albumin	g/L	35 - 55
Blood Urea Nitrogen (BUN)	mmol/L	3.6 - 7.1
Calcium	mmol/L	2.2 - 2.6
Chloride	mmol/L	80 - 115
Corrected calcium	mmol/L	2.2 - 2.6
Glucose	mmol/L	3.9 - 7
Bicarbonate (HCO ₃)	mmol/L	22 - 29
Carbon dioxide	mmol/L	21 - 30
Potassium	mmol/L	3.5 - 5
Magnesium	mmol/L	0.8 - 1.2
Sodium	mmol/L	136 - 145
Phosphate	mmol/L	1 - 1.4
Protein	g/L	55 - 80
Urea	mmol/L	3.6 - 7.1

Appendix B Summary of statistical analyses

Assuming there are 15 patients per arm included in the combination and control arms. The action to either continue or stop the combination arm depends on the number of responder in the combination and control arms respectively. The detailed decision is included below. The x axis represents number of responders in the control arm. The y axis represents number of responders in the combination arm. When action="Continue", the combination arm is recommended to continue; otherwise, it is recommended to stop the combination arm due to lack of confidence to achieve a positive results if the arm is continued.

Appendix C R code for conditional power and stopping boundary calculation

```
## conditional power function; output conditional power
getcp = function( r0, r1 ,m0, m1 ,n0=35, n1=35, SIG.LEVEL = 0.05){
# r0, r1 – number of response in control arm and combination arm at IA, respectively;
# m0, m1 - number of randomized patient in control and combination arm at IA, respectively
# n0, n1 - planed final sample size if the trial is continued for control and combination arm;
# SIG.LEVEL - 1-sided significant level for Fisher’s exact test
p0 = 0.2 #r0/m0
p1 = 0.5 #r1/m1

ilow <- 0
ihigh <- n0 - m0
jlow <- 0
jhigh <- n1-m1
prob.reject = 0
for (i in ilow:ihigh) {
for (j in jlow:jhigh) {
x <- matrix(c(j+r1, n1-(j+r1),i+r0, n0-(i+r0)), 2, 2)
pval <- fisher.test(x, alternative="greater")$p.value
if (pval <= SIG.LEVEL) {
prob.reject <- prob.reject + dbinom(i, n0-m0, p0) * dbinom(j, n1-m1, p1)
}
}}
prob.reject
}

